Study population. Study counsellors will enroll consecutive eligible, consenting pregnant adolescent girls and women (16-40 years old) in antenatal care with singleton pregnancies, without recent PrEP exposure.

- We will enroll a separate cohort of women during singleton pregnancy at 24-30 weeks' gestation followed through postpartum until 6-12 weeks after delivery
- Women will be randomized to TAF vs. TDF and provided with directly observed oral PrEP for 8 weeks with weekly clinic visits and phone video directly observed therapy while pregnant and another 8 weeks of directly observed PrEP in postpartum period
- Women will serve as their own controls to compare their drug levels in pregnancy vs. postpartum periods
- The study will also allow for women who are enrolled and then lost to follow up to be re-enrolled into the study at a later time if they still comply with all inclusion criteria.

Sample Size: A target sample size of at least 15 women per group is consistent with similar studies of directly observed PrEP that estimated steady-state concentrations of TFV-DP, providing adequate precision for outcome estimates.¹³ We increased the sample size to 35 participants per group to account for potential attrition (total N=70 women). This study is not powered to assess safety or efficacy.

Inclusion Criteria:

1. ≥ 18 years old
2. confirmed HIV-negative (confirmed with a 4th generation antigen HIV test) at time of study entry
3. Attending ANC visits at Gugulethu MOU, NY1 Clinic or Vuyani Clinic
4. confirmed to be 20-30 weeks pregnant
5. without psychiatric or medical contraindications to PrEP
6. estimated creatinine clearance (CrCl) >60 mL/min
7. resides close to clinic (<10 km)
8. has a smart phone that can take video footage (with data bundle from study)
9. agrees to provide video phone footage of taking a pill a day for 8 weeks during pregnancy and again for 8 weeks in postpartum period
10. Previously lost to follow up participants who wish to be re-enrolled in the study so long as they still meet all of the above inclusion criteria.

Exclusion criteria:

Individuals not meeting the above criteria or meeting any of the following criteria will be excluded:

1. Concurrent enrolment in another HIV-1 vaccine or prevention trial
2. Currently taking PrEP or taken in last 90 days (except in cases of re-enrollment of previously lost to follow up participants)
3. History of renal disease
4. Current clinical diagnosis of hypertension

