Eligible, consenting women will receive up to R250 (~\$15) in grocery vouchers, transportation and refreshments per weekly visit for their time and effort in the study as well as transportation to the facility. All participants will also receive data bundles of 1GB at enrolment and 10GB every month thereafter for the duration thri follow up to send videos of them taking daily PrEP. During weekly visits, participants will receive minor refreshments (e.g. sandwich and cool drink).

Procedures for the informed consent process are outlined below. Throughout, trained study staff will ensure that women are aware of their right to refuse and/or withdraw from the study at any time. In addition, study staff will emphasize that all study activities are entirely separate from routine ANC and postnatal care services received and that refusal or withdrawal from the study will have no impact on their ability to access any services provided at any public-sector health facility.

Trained study counsellors will recruit n=70 women that are 20-30 weeks pregnant and NOT part of the ongoing PrEP-PP study for the PK sub-study. Participants will be screened for HIV infection; only those who test negative will be eligible to initiate once-daily FTC/TDF or FTC/TAF for PrEP. Participants must be willing to initiate and take PrEP and to take videos and send to the study for daily adherence for 8 weeks in pregnancy and again for 8 weeks postpartum. Women will be invited to participate in the study through ~2-3 months postpartum (depending on when they start the 8 week postpartum DOT). Women will be randomized into the TDF vs. TAF arm. Women will provide their own controls, providing pregnant and postpartum samples.

- **TDF Arm :** Women will receive a fixed dose combination of 200 mg emtricitabine (FTC) and 300 mg tenofovir disoproxil fumarate (TDF) administered once daily under direct observation for 8 weeks during pregnancy and again for 8 weeks in postpartum period
- **TAF Arm:** Fixed dose combination of 200 mg emtricitabine (FTC) and 25 mg tenofovir alafenamide (TAF) administered once daily under direct observation for 8 weeks during pregnancy and again for 8 weeks in postpartum period
- **At study end:** Participants in both arms will be given a 3 months supply of Tenemine (FTC200mg/TDF300mg).

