Study Duration: Approximately 12 months total for this component. Analysis of PrEP (TAF vs TDF) drug levels will be completed within approximately three months after the last participant follow-up visit. The duration is shorter because we have ongoing cohort recruitment ongoing in Gugulethu, NY1 and Vuyani and can recruit 70 women who reside close to the clinic within 2-3 months.

Study procedures: Weekly (see **Table 2** for scheduled events), following PrEP initiation a maternal blood specimen will be collected via venepuncture (at home or in clinic, depending on participant's preference). This specimen will be used to create a DBS specimen to be tested at the laboratory at the University of Colorado. DBS cards will be prepared and stored following standard protocols and stored at -80°C for shipment and analysis at the end of the study with the clinical pharmacoanalytic laboratory of [name] at University of Colorado, Denver (funding proposal under separate cover).

Enrolled maternal participants can continue to take PrEP through delivery and postpartum period to prevent HIV during this time. Pregnancy and postpartum periods are associated with elevated risk for HIV acquisition. As such, the study aims to evaluate the different levels of TAF vs TDF associated with once-daily FTC/TDF regimen vs FTD/TAF regimen. Study staff will monitor and document maternal participants' daily administration of the study drug.

Only doses directly observed in-person or via video call by study staff or sent video recordings will be considered adequate documentation of the PrEP doses taken for the purposes of defining an evaluable participant (see Analytics).

These data will be used to determine the drug thresholds for understanding of TAF vs TDF adherence measures. The drug threshold corresponding to adequate adherence will be defined from the distribution of steady-state TFV-DP concentrations at antenatal vs postnatal visits.

If up to 3 PrEP doses were not directly observed, a urine test will be done to detect the presence of tenofovir metabolite in the participant's system prior to the drawing of blood samples.

We will evaluate the 'tail' (plasma and intracellular) of TFV and TFV-DP in the PrEP setting, comparing TAF to TDF and TAF and TDF levels in pregnant to postpartum women. See SOPs for dried milk spots (DMS) and dried blood spot (DBS) collection in Appendix.

- Plasma PK (TFV) – 8 samples in pregnancy, and 8 samples in postpartum (1 per week)

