Primary Objective: To establish benchmarks of TFV-DP concentrations following daily dosing with TAF vs TDF in pregnancy and again in postpartum

Secondary Objectives: To compare the difference with TFV-DP with TDF and TAF for pregnancy against postpartum and to establish benchmarks of TFV-DP in breastmilk in postpartum women and compare with TDF arm.

Prior to conducting analyses, the study team, including the study Pharmacologists, will review the pattern of completeness of each participant's directly observed PrEP therapy (via video call) to ascertain if all 8 weeks were taken daily in antenatal and postnatal care to determine suitability for inclusion in the analysis. In each of the groups (TDF vs TAF in antenatal and postpartum groups), the distributions of steady state concentration (Css) defined as the TFV-DP concentration observed will be summarized.

For each group, we will plot median and interquartile range (IQR) TFV-DP concentrations for each week and fit a Loess curve and 95% confidence interval (CI) to the concentration-time data. The plateau in the concentration-time curve was assumed to represent steady-state. Tenofovir diphosphate at week 8 (steady-state) will be analyzed as median, IQR, mean, standard deviation (SD), and 95% CI in the pregnancy and postpartum groups by study arm. The Wilcoxon rank-sum test will be used to evaluate differences in the distribution of 8-week concentrations between groups. Additionally, a nonlinear mixed-effects population PK model will be fit to the TFV-DP data using a 1-compartment constant input model using Phoenix (Certara, Princeton, NJ). The model will be used to summarize PK parameters for both groups and between TDF and TAF arms.

Differences between the antenatal and postpartum group intra-individual comparison of plasma TDF concentrations will be evaluated using two sample t-tests. We will evaluate bio-equivalence in plasma TFV-DP between TAF and TDF in pregnant and postpartum women.

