The PK testing laboratory will provide drug level results by study arm, comparing TAF to TDF in pregnancy and again in postpartum periods in the same women. The secondary objective is to compare the difference in TFV-DP in pregnancy against postpartum samples in the TAF vs TDF group. We will compare with reference ranges as it relates to the categorized level of adherence to use during adherence counselling sessions. The reference ranges will include approximately three adherence categories, aligned with other similar studies in the field. Finally, we will evaluate the level of TFV-DP in breastmilk in postpartum women and compare with TFV-DP in the TDF arm.

Qualitative Data:

- At the final study visit, participants will be asked to answer a few questions about their experience and perceptions of taking video observed PrEP doses.
- This will be done during a 20 minute exit interview.
- Participants will be asked to select a rating, from a scale, that best reflects their perceptions of the convenience, privacy, and ease of use the video observation process
- Participants will also be asked open ended questions about what they perceive to be barriers and facilitators of the video observation process.
- All answers will be anonymized by assigned ID numbers (PIPs)

Safety:

There are no indications that metabolism of TAF, TDF and TFV is sensitive to genetic polymorphisms. Population-based PK analyses indicated that race is not a clinically relevant covariate. Exposure of TAF/TFV was negligible in breastmilk.

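### The within-woman pregnancy-versus-postpartum plasma comparison is assigned an independent-samples t-test, and no paired analysis is named anywhere in the plan

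*Combined protocol and SAP*

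**What the plan says.** The design is own-control. Study population (section 2) says: "Women will serve as their own controls to compare their drug levels in pregnancy vs. postpartum periods". Enrolment procedures repeats it: "Women will provide their own controls, providing pregnant and postpartum samples". The ANALYTICS section describes the laboratory results as "comparing TAF to TDF in pregnancy and again in postpartum periods in the same women".

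For plasma, Study procedures plans "comparing TAF to TDF and TAF and TDF levels in pregnant to postpartum women", with eight weekly samples in each period. Both that list and Table 2 give the plasma analyte as TFV. The test is in ANALYTICS: "Differences between the antenatal and postpartum group intra-individual comparison of plasma TDF concentrations will be evaluated using two sample t-tests". No week or summary of the eight samples is specified.

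For TFV-DP, the objective is explicit: "The secondary objective is to compare the difference in TFV-DP in pregnancy against postpartum samples in the TAF vs TDF group". The only hypothesis test named is: "The Wilcoxon rank-sum test will be used to evaluate differences in the distribution of 8-week concentrations between groups". A nonlinear mixed-effects population PK model is also planned for TFV-DP. Its stated use is to summarise PK parameters, and no period contrast is specified.

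**The concern.** The plasma sentence contradicts itself. It calls the comparison intra-individual and then names a test for independent samples. A programmer following it would discard the link between each woman's two values, which is what own-control sampling is there to provide. The confidence interval for the period difference would then have the wrong width whenever the two values are correlated.

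The TFV-DP contrast is less clear-cut, because the meaning of groups in the rank-sum sentence is open:

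- The sentence just before it, and the one on the use of the PK model, use the word for periods and arm for treatment.
- An earlier ANALYTICS sentence uses it for arm-by-period sets.
- Sample Size, Table 1 and the later statement of the secondary objective use it for treatment arms.

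If groups are periods, the rank-sum also ignores pairing. If they are arms, the test is valid and the secondary period comparison simply has no named test.

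**Working it through.** **Plan's own figures.** There is no power calculation to reproduce. Sample Size gives at least 15 women per group, raised to 35 for attrition, and 2 × 35 = 70 agrees with the stated total. No SD, within-woman correlation or attrition rate is given.

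**Inputs.** n = 15 and 35 per arm come from Sample Size. The 31% reduction is the lower end of the 31–37% in section 1.1; it is a TFV-DP figure and is borrowed for illustration, since no plasma period effect is given. Assumed: bivariate normal log concentrations, one value per woman per period, log SD σ = 0.4 or 0.6, correlation ρ from 0 to 0.7, two-sided alpha 0.05.

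**Standard error, complete pairs, equal variances.**
- Two-sample: σ√(2/n).
- Paired: σ√(2(1 − ρ)/n).
- Ratio: 1/√(1 − ρ) = 1.00, 1.20, 1.41, 1.83 at ρ = 0, 0.3, 0.5, 0.7.

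With 15 pairs and no effect, the nominal 5% two-sample test rejects about 2.1%, 0.8% and 0.1% of the time at ρ = 0.3, 0.5, 0.7 (simulation). The paired test stays at about 5%.

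**Power, ρ = 0.5, difference −ln(0.69) = 0.3711.** Paired power is from the noncentral t with n − 1 df; two-sample power is simulated.

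| Pairs | Log SD | Two-sample SE | Paired SE | 0.3711 / paired SE | Two-sample power | Paired power |
|---|---|---|---|---|---|---|
| 15 | 0.4 | 0.1461 | 0.1033 | 3.59 | 75% | 92% |
| 35 | 0.6 | 0.1434 | 0.1014 | 3.66 | 79% | 94% |
| 35 | 0.4 | 0.0956 | 0.0676 | 5.49 | 99.6% | 99.96% |

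**If women seen in one period are kept.** Take, as an assumption, 35 pregnancy values and 15 postpartum values, the 15 being from the same women.

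- *Unequal variances* (log SD 0.4 in pregnancy, 0.6 postpartum, ρ = 0.3). The pooled variance is (34 × 0.16 + 14 × 0.36)/48 = 0.2183, so the test uses √[0.2183 × (1/35 + 1/15)] = 0.144. The true standard error is √[0.16/35 + 0.36/15 − 2 × 0.3 × 0.4 × 0.6/35] = 0.156. The test's standard error is now too small, and its type I error is about 7% (simulated). At ρ = 0 it is about 9.5%.
- *Equal variances* (log SD 0.4, 31% effect). Two-sample versus paired power is 84% versus 66% at ρ = 0, 86% versus 81% at ρ = 0.3, and 88% versus 92% at ρ = 0.5. With few pairs and low correlation, the paired test loses.

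**The case against.** The wording may be loose, with two samples meaning two samples per woman. If so, the correction costs a phrase, but as written the term denotes the independent-samples test.

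The population PK model could carry within-woman correlation. It could, if both periods were fitted jointly with a period effect. The plan does not say so, and the model covers TFV-DP rather than plasma.

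The explicit error concerns plasma, which is not a listed objective, and the size of the loss rests wholly on assumed SDs and correlations. Both points stand and hold the severity down. The loss lies anywhere between none (ρ = 0, or ample pairs with a large effect) and substantial.

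A reader might infer that the TFV-DP period test is equally wrong. The documents do not support that, because the arm reading of groups is tenable and makes the rank-sum valid.

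A reader might also infer that the error can only be conservative. That holds for complete pairs with positive correlation. It need not hold if one-period women are kept and variances differ, as the 7% figure shows (for the equal-variance form of the test). Whether such women are kept is unsettled: the completeness review in ANALYTICS can be read as requiring all eight weeks in both periods, which would leave complete pairs only.

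**Conclusion.** The plasma period comparison is wrong as written: the named test contradicts both its own label and the own-control design, and no paired procedure is named anywhere. For TFV-DP the fault is conditional. It is either a second unpaired test or a secondary contrast with no named test.

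With complete pairs and positive correlation, the result is an interval that is too wide and lost power: 17 percentage points in the 15-pair example (92 − 75), 15 points with 35 pairs at log SD 0.6 (94 − 79), and almost nothing with 35 pairs at log SD 0.4. All of this rests on assumed SDs and correlations and a borrowed effect size.

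It does not follow that the trial's main results are compromised. The primary benchmarks are descriptive and do not depend on this test. This should be fixed, at the low end of that category.

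**What to change.** In ANALYTICS, replace the two-sample t-tests with a paired analysis within each arm, on women evaluable in both periods. Use either a paired t-test on log concentrations, reported as a geometric mean ratio with 95% CI, or the Wilcoxon signed-rank test. Apply the same analysis to the week-8 TFV-DP pregnancy-versus-postpartum comparison. State that the rank-sum test is for TAF versus TDF within a period only. Correct the plasma analyte to TFV, and name the plasma week or summary used.

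Optionally, to use women evaluable in only one period, add a mixed model with period, arm, period × arm and within-woman correlation, allowing a separate variance for each period. A common-variance model should not be assumed safe when the two periods have unequal numbers.

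The cost is SAP wording and minor programming, with no new data, samples or participants. The downside is that one-period women do not contribute to the paired test, which can then have less power than the two-sample test if many drop out and correlation is low (66% versus 84% in the 35/15 case at ρ = 0).

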2. STUDY

Study aims. (1) To establish benchmarks of TFV-DP concentrations as measures of adherence following daily dosing with TAF vs TDF in pregnancy and again in postpartum; (2) To compare the difference of TFV-DP within TDF and TAF for pregnancy vs. postpartum, and to establish adherence benchmarks of levels of TFV-DP in breastmilk in postpartum women comparing the TAF and TDF samples.

Setting. The study will take place in urban townships in Cape Town (Gugulethu, NY1 and Vuyani) with high HIV incidence that spans the different socioeconomic, cultural, and ethnic groups in South Africa. We selected this community because of the high HIV prevalence there in pregnant and breastfeeding women, and because of the high number of mothers visiting every month for ANC and labour/delivery. Further, our team has several years' experience implementing research studies in this clinic which will facilitate the integration of the study there. Our study on PrEP in pregnancy ("PrEP-PP"; NIMH R01MH11677, NCT03826199) is one of the first studies to integrate PrEP into maternal child health care in South Africa and will provide the platform from which to recruit for the PK sub-study.

In 2019, the Gugulethu Midwife Obstetric Unit (MOU) saw over 3300 new ANC consultations per month, and 72% (n=2300) are HIV-negative. Considering our experience and patient flow, we are confident that at least 60 women/month per facility can be enrolled. Further, Drs. [name] and [name] have conducted research in the Gugulethu community for more than a decade and have substantial experience partnering with local health services. Building on this platform, we will use existing infrastructure in each clinic, including capacitating existing clinical providers, pharmacists and counsellors, to

provide PrEP care to pregnant and breastfeeding mothers. We will hire study staff to assist in the coordination, data management, and overall quality assurance of the drug provision, phlebotomy, and follow up.

COVID-19 and study implications. Our PrEP-PP study has continued during the COVID-19 lockdown in South Africa because it is considered to be an essential service. We continue to recruit over 15 women/week and have over 20 study retention visits in pregnant and postpartum women (telephonic and in person) during the COVID lockdown. We observe all University of Cape Town and Department of Health COVID-19 infection prevention and control methods.

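### The secondary objective is worded three ways, and no planned analysis specifies the within-woman pregnancy-postpartum change in TFV-DP that it needs, either within or between arms

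*Combined protocol and SAP*

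**What the plan says.** The objective appears in three places in the combined protocol and SAP:

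- Section 2, Study aims, Aim 2: "To compare the difference of TFV-DP within TDF and TAF for pregnancy vs. postpartum". This reads as a period comparison inside each arm.
- ANALYTICS, Secondary Objectives: "To compare the difference with TFV-DP with TDF and TAF for pregnancy against postpartum". This could mean within-arm or between-arm.
- ANALYTICS, the paragraph on laboratory results: "The secondary objective is to compare the difference in TFV-DP in pregnancy against postpartum samples in the TAF vs TDF group". This reads as a comparison of the period difference between TAF and TDF.

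The design is paired. Women are randomised to one drug and take it in both periods, and under Study population: "Women will serve as their own controls to compare their drug levels in pregnancy vs. postpartum periods".

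The analyses planned under ANALYTICS that could bear on the objective are:

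- Descriptive summaries of week-8 TFV-DP: "mean, standard deviation (SD), and 95% CI in the pregnancy and postpartum groups by study arm", alongside medians and IQRs.
- One test of week-8 levels: "The Wilcoxon rank-sum test will be used to evaluate differences in the distribution of 8-week concentrations between groups".
- A nonlinear mixed-effects population PK model of TFV-DP: "The model will be used to summarize PK parameters for both groups and between TDF and TAF arms".
- One period comparison, on plasma: "Differences between the antenatal and postpartum group intra-individual comparison of plasma TDF concentrations will be evaluated using two sample t-tests".
- A bioequivalence evaluation of TAF against TDF in pregnant and in postpartum women, and laboratory results that compare the arms in each period in turn.

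**The concern.** A study in which each woman is measured on one randomised drug in both periods can answer two questions about pregnancy. How much lower is TFV-DP in pregnancy on each drug? Is the proportional change the same on both? The first needs a paired comparison within arm. The second needs the between-arm difference in the paired change, that is, the arm-by-period contrast. If neither is specified, the plan could be followed exactly and still leave its secondary objective without a matching result.

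The scale also matters. If TFV-DP levels differ r-fold between the arms, the same percentage fall in both gives raw differences that differ r-fold. A comparison of raw differences could then suggest a drug effect where the proportional change is identical.

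**Working it through.** **Step 1. Match each planned analysis to the two readings.**

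| Planned analysis | Paired within-arm TFV-DP change? | Between-arm difference in that change? |
|---|---|---|
| Week-8 summaries by period and arm | No: separate cells | No |
| Wilcoxon rank-sum | No: unpaired, compares levels | No |
| Population PK model | Not specified: no period covariate named | Not specified: no arm-by-period term named |
| t-tests, antenatal vs postpartum | No: two-sample, and on plasma | No |
| Bioequivalence, TAF vs TDF | No: compares levels between arms | No |

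The t-test sentence is the only one that mentions an intra-individual comparison, but it names a two-sample test and does not cover TFV-DP.

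**Step 2. Inputs.**

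- Sample size (section 2, Sample Size): at least 15 per group, raised to 35 per group for attrition. The stated total checks: 2 × 35 = 70. No attrition rate is given. Going from 15 to 35 would correspond to 1 − 15/35 = 57% loss, so 15 and 35 are taken as the limits for evaluable women per arm.
- Size of the pregnancy effect (section 1.1): TFV-DP 31-37% lower in pregnancy, from separate groups of 20 pregnant and 20 postpartum women. This gives pregnancy:postpartum ratios of 0.69 and 0.63.
- SD of the within-woman log ratio: not in the documents. Assumed to be 0.3 to 0.6.
- Two-sided 5% level: assumed, in line with the 95% CIs in ANALYTICS.

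**Step 3. What the planned data could deliver.** Let d be a woman's log(pregnancy/postpartum) week-8 TFV-DP.

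- Within-arm ratio: CI factor = exp[t(0.975, n−1) × SD/√n]. This is ×/÷ 1.18 (SD 0.3) to 1.39 (SD 0.6) at n = 15, and 1.11 to 1.23 at n = 35.
- Ratio of ratios: CI factor = exp[t(0.975, 2n−2) × SD × √(2/n)].
  - n = 15, SD 0.3: exp(2.048 × 0.3 × 0.365) = 1.25; SD 0.6: 1.57.
  - n = 35, SD 0.3: exp(1.995 × 0.3 × 0.239) = 1.15; SD 0.6: 1.33.
- Ratio of ratios detectable with 80% power (noncentral t): 1.37 to 1.89 at n = 15 and 1.23 to 1.50 at n = 35, or the inverse.

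**Step 4. Why two separate within-arm tests are not a substitute.** Suppose both drugs have the same true fall and each arm is tested with a paired t-test. With power p in each arm, exactly one arm is significant with probability 2p(1−p). Example: ratio 0.69, SD 0.6, n = 15 gives noncentrality 0.371/(0.6/√15) = 2.40, p = 0.606, and 2 × 0.606 × 0.394 = 0.48.

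| Fall | n per arm | SD 0.3 | SD 0.4 | SD 0.5 | SD 0.6 |
|---|---|---|---|---|---|
| 31% | 15 | 1% | 15% | 36% | 48% |
| 37% | 15 | 0% | 3% | 16% | 33% |
| 31% | 35 | 0% | 0.1% | 2% | 10% |
| 37% | 35 | 0% | 0% | 0.1% | 1% |

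A direct test of the contrast would hold this error at 5% whatever the SD.

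**The case against.** The strongest reply is that only a within-arm comparison was meant. Aim 2 says so most clearly, and the stated purpose of the pairing is to compare each woman's levels between periods, not to compare changes between drugs. Even the third wording could be stretched to mean the period difference in each arm's group. This stands as far as it goes: the documents do not settle the objective as a between-arm comparison, and a reader should not infer that they do. It does not close the gap, because a paired TFV-DP analysis within arm is not planned either.

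Second, the population PK model covers TFV-DP in both arms and could carry the contrast. It could, if arm, period and their interaction were entered as covariates. The text says only that it summarises parameters, so this is a route to the remedy and not a plan already in place.

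Third, the study is largely descriptive and small, and the contrast could be added at analysis without new data. That is fair. It argues for an interval instead of a powered test, and it limits the seriousness of the point, but it does not argue for leaving the estimand undefined.

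A reader might also infer that the sponsor will judge the drugs by eye, or by one arm being significant and the other not. No sentence says so, and the paired TFV-DP tests behind the Step 4 rates are themselves not planned. Those rates show why such a shortcut should be avoided. They do not describe the plan.

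**Conclusion.** The point holds in a limited form. The three wordings need reconciling. On the between-arm wording, no planned analysis estimates the difference between TAF and TDF in the within-woman change; on the within-arm wording, no paired TFV-DP analysis is specified. This conclusion comes from the text alone and depends on no assumed number.

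The size of the consequence does depend on assumptions. For the 31-37% fall quoted in the protocol and SD 0.3 to 0.6, comparing separate within-arm tests would give one significant arm out of two in about 0-48% of trials at 15 per arm and 0-10% at 35, with no true drug difference. A general statement that the false-claim rate is far above 5% is therefore not supported: in several of these cases it is below 5%. The SD and the evaluable number are not in the documents, and the quoted fall comes from separate groups and not from within-woman change.

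It would also be wrong to conclude that the design cannot answer the question. The planned week-8 samples are sufficient to estimate the contrast, though with limited precision.

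**What to change.** 1. Choose one wording of the secondary objective and use it in Study aims, in the Secondary Objectives and in the later ANALYTICS paragraph. State whether the target is the within-arm change, the between-arm difference in change, or both.
2. Pre-specify a linear mixed model of log week-8 TFV-DP with arm, period, arm × period and a random woman effect. Alternatively, name the equivalent covariates in the population PK model.
3. Report the pregnancy:postpartum ratio in each arm, and the ratio of those ratios (TAF vs TDF), each with a 95% CI. Label them as estimation, since the sample size has no power basis for this contrast.
4. State that women with only one evaluable period stay in the model, and the missing-data assumption (missing at random) that this requires.

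No extra samples or visits are needed. The cost is SAP wording and a little analysis work. The downside is a wide interval, about ×/÷ 1.25 to 1.57 if only 15 women per arm are evaluable, which is an honest account of what the trial can say about a difference between the drugs.
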